## The following changes were reviewed and approved by the IRB:

Participants will be asked to complete required COVID testing (e.g. via nasopharyngeal swab) prior to procedures, such as the Cardiopulmonary Exercise Test (CPET). This follows current hospital safety guidelines and protocols as put forth by the CPET laboratory.

A revised Detailed Protocol, Version Date: 08/14/2020; Protocol Summary, Version Date: 08/14/2020; an informed consent, and recruitment materials reflect the changes made.

NOTE TO THE PI: Thank you for the updates, which could be communicated to active participants without formal reconsent.

- 1. Submission of any and all proposed changes to this project (e.g., protocol, recruitment materials, consent form, status of the study, etc.) to the IRB for review and approval prior to initiation of the change(s), except where necessary to eliminate apparent immediate hazards to the subject(s). Changes made to eliminate apparent immediate hazards to subjects must be reported to the IRB as an unanticipated problem.
- 2. Submission of a continuing review submission or institutional status report as required by the IRB and/or institution to continue the research, and submission of a final report when the project has been closed or completed.
- 3. Submission of any and all unanticipated problems, including adverse event(s) in accordance with the IRB's policy on reporting unanticipated problems including adverse events
- 4. Obtaining informed consent from subjects or their legally authorized representative prior to initiation of research procedures when and as required by the IRB and, when applicable, documenting informed consent current IRB approved consent form(s) with the IRB-approval stamp in the document footer.

Mass General Brigham [name]

[contact] [contact]

- 5. Informing all investigators and study staff listed on the project of changes and unanticipated problems, including adverse events, involving risks to subjects or others.

## The following changes were reviewed and approved by the IRB:

- 1) Eligibility CRF was updated to include "lactating/nursing" in exclusion criteria. This reflects the current protocol and informed consent, which excludes enrollment of women who are lactating/nursing, pregnant, or planning to become pregnant while participating in the study.
- 2) Laboratory units on Visit 3 CRF were updated.
- 3) Listed side effects on Visit 3, 4, and 5 CRFs were updated for clarity, as "nausea" had appeared twice in the list.

- 1. Submission of any and all proposed changes to this project (e.g., protocol, recruitment materials, consent form, status of the study, etc.) to the IRB for review and approval prior to initiation of the change(s), except where necessary to eliminate apparent immediate hazards to the subject(s). Changes made to eliminate apparent immediate hazards to subjects must be reported to the IRB as an unanticipated problem.
- 2. Submission of a continuing review submission or institutional status report as required by the IRB and/or institution to continue the research, and submission of a final report when the project has been closed or completed.
- 3. Submission of any and all unanticipated problems, including adverse event(s) in accordance with the IRB's policy on reporting unanticipated problems including adverse events.
- 4. Obtaining informed consent from subjects or their legally authorized representative prior to initiation of research procedures when and as required by the IRB and, when applicable, documenting informed consent current IRB approved consent form(s) with the IRB-approval stamp in the document footer.
- 5. Informing all investigators and study staff listed on the project of changes and unanticipated problems, including adverse events, involving risks to subjects or others.

Mass General Brigham [name]

[contact] [contact]

Cardiometabolic Disease and Pulmonary Hypertension

NCT03349775

Document Version 1/15/2021

Statistical Analysis Plan

For METCPET clinical trial interim analysis

Distributions and outliers of continuous variables will be examined using histograms and Whisker box plots. Variables with skewed distribution will be natural log-transformed to approximate normal distribution. Outliers detected by box plots will be examined case-by-case to ensure no data input errors. Categorical variables (race and ethnicity) will be checked manually in all subjects (n=15). Covariate data including age, sex, race/ethnicity, height in inches, weight in pounds, Body Mass Index (BMI), heart rate, systolic blood pressure, diastolic blood pressure will be summarized and reported in mean (Standard Deviation) for continuous variables and frequencies (percentage) for categorical variables. Between-group differences will be compared using two independent samples t-test or Fisher's exact test as appropriate.

We will calculate PAP/CO slope by using serial pulmonary artery pressure (PAP) and cardiac output (CO) measurements before and after Metformin treatment for each randomized subject. Change in PAP/CO slope will then be generated by subtracting pre-treatment PAP/CO from post-treatment PAP/CO. The primary analysis will be between-group comparisons in PAP/CO slope change pre- and post-treatment in an intention-to-treat analysis using Welch's t-test or Two independent samples t-test depending on the variances in both groups. We will also conduct secondary analysis on other hemodynamic and gas exchange variables with the same procedures. Mean change differences between groups will be reported with 95% confidence interval, and between-group PAP/CO slope changes and mean PAP changes will be visualized using Whisker box plots. P values are two-sided with a significance level of 0.05. All statistical analyses will be performed in SAS 9.4 (Cary, NC).

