Statistical analyses for Aim 3: We will compare the change in  $\Delta mPAP/\Delta CO$  slope in the metformin vs placebo groups. The "delta" in slope will be defined as the 3-month minus the baseline value. We will apply a two-sample t-test to compare the delta in the two groups in an unadjusted intention-to-treat analysis. An adjusted analysis will be performed using a multivariable random effects linear regression model adjusted for baseline  $\Delta mPAP/\Delta CO$ , such that [delta  $\Delta mPAP/\Delta CO$ ] = intercept +  $\beta_1$ \*treatment group +  $\beta_2$ \* $\Delta mPAP/\Delta CO_{baseline}$ , with treatment group and  $\Delta mPAP/\Delta CO_{baseline}$  as fixed effects and treatment group modeled as a random effect. Given that the randomization will be stratified by type of pulmonary vascular dysfunction (resting versus exercise-induced), we will use a 'strata' statement to indicate PH type in the model. We anticipate that metformin will improve PAEC insulin resistance (% change in the ratio of p-eNOS to total eNOS) and also pulmonary hemodynamics. In secondary analyses, we will examine the correlation between PAEC and venous endothelial cell insulin resistance among treatment groups.

Statistical power for Aim 3: We will power the study for the between-group comparison (metformin vs placebo) of the delta in  $\Delta$ mPAP/ $\Delta$ CO (3 month – baseline). In 15 prior patients with repeat testing within 12 weeks, the reproducibility of  $\Delta$ mPAP/ $\Delta$ CO was robust, with an intra-individual CV of 0.92, and a standard deviation (SD) of the delta (12-week minus baseline) of 0.46. We will assume a similar SD in this study. In our experience with intervention studies, attrition from non-compliance is ~15%. With a target enrollment of 75 participants and 15% loss to follow-up, we would have 64 participants completing the study. In preliminary studies, the difference in  $\Delta$ mPAP/ $\Delta$ CO slope among diabetics and non-diabetics was 0.7mmHg/L. We estimate >80% power to detect up to 50% of the difference in  $\Delta$ mPAP/ $\Delta$ CO between diabetics vs nondiabetics (0.35mmHg/L) among the treatment groups using a two-sided t-test with 5% type I error.

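### The SAP tests change in PAP/CO slope and every secondary variable by unadjusted t-test only and does not carry forward the protocol's baseline-adjusted analysis; the gain from restoring it is small for the slope and belongs at the final analysis.

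*SAP*

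**What the plan says.** Protocol, Section 6, Aim 3, describes two analyses of the change in slope from baseline to 3 months. The first: "We will apply a two-sample t-test to compare the delta in the two groups in an unadjusted intention-to-treat analysis". The second: "An adjusted analysis will be performed using a multivariable random effects linear regression model adjusted for baseline" slope, with type of pulmonary vascular dysfunction also brought in through a strata "statement to indicate PH type in the model". Neither is labelled primary. The power statement that follows is for the unadjusted comparison, "using a two-sided t-test with 5% type I error".

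The SAP is headed as the plan for the interim analysis and refers to 15 subjects. It says: "The primary analysis will be between-group comparisons in PAP/CO slope change pre- and post-treatment in an intention-to-treat analysis using Welch's t-test", or the equal-variance t-test, depending on the variances. Other hemodynamic and gas exchange variables follow the same procedures. Mean differences in change are reported with 95% confidence intervals, and "P values are two-sided with a significance level of 0.05". Age, sex, BMI and other covariates are summarized and compared between groups, but no analysis in the SAP uses a baseline value as a covariate. No plan for the final analysis is among the documents.

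**The concern.** A raw change score fixes the coefficient of the baseline value at 1. If the correlation r between baseline and follow-up is below 1, a fraction (1 − r) of any chance baseline difference between arms stays in the estimated effect. A model that includes baseline slope estimates that coefficient and, in large samples, has a variance no greater than that of the change score. Baseline slope is measured before randomization, is already needed to compute the change, and is the variable the protocol itself chose for adjustment.

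Two things are at stake. One is some precision at the final analysis, mainly for variables that repeat less well than the slope. The other is pre-specification. The protocol offers two estimates without ranking them and the SAP describes only one. If the adjusted result is first produced after unblinding, the choice between the two is open to question.

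**Working it through.** **Inputs.**
- SD of the change in slope: "a standard deviation (SD) of the delta (12-week minus baseline) of 0.46", from 15 prior patients (protocol, Section 6, Aim 3).
- Cross-sectional SD of the slope: 1.3 in each preliminary group (Section 6, Aim 2).
- Target difference 0.35; 75 enrolled with 15% loss, so 75 × 0.85 = 63.75, or 64 completers; 1:1 allocation (Sections 4 and 6).
- Interim n = 15 (SAP). A 7/8 split is assumed.
- Equal variances at the two visits are assumed.

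**The protocol's own figure.** SE = 0.46 × √(2/32) = 0.115. Power for 0.35 at two-sided 0.05 is 85.0% (noncentral t) or 86.1% (normal approximation). The stated figure of more than 80% reproduces.

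**Correlation and variance ratio.**
- r = 1 − 0.46² / (2 × 1.3²) = 1 − 0.2116/3.38 = 0.937.
- Adjusted/unadjusted variance before estimation cost: (1 + r)/2 = 0.969.
- Estimating the baseline coefficient multiplies variance by 1 + 1/(N − 4): 61/60 = 1.017 at N = 64 and 12/11 = 1.091 at N = 15. One further degree of freedom is lost.

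**Pessimistic SD of the change.** An SD estimated on 14 degrees of freedom has upper 95% limit 0.46 × √(14/5.629) = 0.73. Then r = 1 − 0.5329/3.38 = 0.842 and (1 + r)/2 = 0.921.

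| SD of change | N | Net variance ratio | Power unadjusted | Power adjusted |
|---|---|---|---|---|
| 0.46 | 64 | 0.969 × 1.017 = 0.985 | 85.0% | 85.5% |
| 0.73 | 64 | 0.921 × 1.017 = 0.937 | 47.1% | 49.6% |
| 0.46 | 15 | 0.969 × 1.091 = 1.057 | 27.6% | 26.1% |
| 0.73 | 15 | 0.921 × 1.091 = 1.005 | 13.8% | 13.6% |

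Simulation at SD 0.46 (40,000 trials per setting) agrees: 84.8% and 85.4% at 64; 27.4% and 26.4% at 15. Type I error was about 5% for both methods.

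**If the Aim 3 baseline SD is not 1.3.** The documents do not give it. Two assumed cases point in different directions.
- Everyone selected on slope above 3.0 (the upper end of the normal range in Section 1) from a distribution with mean 2.6 and SD 1.3. The selected baseline variance is about 0.51. Ratio = 1.69(1 − r²) / [1.69(1 − r²) + (1 − r)² × 0.51] = 0.990 at r = 0.937 and 0.975 at r = 0.842. Multiplied by 1.017, these are 1.007 and 0.991, so the gain is about nil.
- SD of change held at 0.46 with a smaller baseline SD, meaning poorer repeatability. Baseline SD 0.8 gives net ratio 0.933 at 64 (power 87.3%) and 1.001 at 15. Baseline SD 0.5 gives 0.802 at 64 (91.7%) and 0.860 at 15.

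**Chance imbalance.** At 7/8, one standard error of baseline difference is 1.3 × √(1/7 + 1/8) = 0.673. The change score carries (1 − r) of it: 0.063 × 0.673 = 0.042, or 0.158 × 0.673 = 0.106 in the pessimistic case. The SE of the change-score difference is 0.46 × √(15/56) = 0.238, or 0.378. The shift is therefore 18% or 28% of one SE. At 64 it is 0.063 × 0.325 = 0.020.

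**Secondary variables.** The documents give no repeatability. For assumed r = 0.5, the net ratio at 64 is 0.75 × 1.017 = 0.763; for r = 0.7, it is 0.85 × 1.017 = 0.864. Variance falls by 24% and 14%.

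**The case against.** The strongest case for leaving the plan alone is that the SAP follows the protocol. A reader might infer that the primary test was switched. The documents do not support that: the unadjusted t-test on change is listed first and is the test that was powered. A t-test on change is valid in a randomized trial.

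A reader might also infer that the SAP gives up free precision and that this matters most at 15 subjects. The arithmetic says otherwise. At 64 the gain on the slope is about half a power point. At 15, with a baseline SD of 1.3, the cost of estimating the coefficient cancels or outweighs it.

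A third tempting reading is that the t-test wrongly attributes baseline imbalance to metformin. At r = 0.937 the change score already removes about 94% of any imbalance. The remainder is chance error inside the standard error and the 95% confidence interval that the SAP reports. It is not bias.

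Finally, the SAP covers the interim only and does not withdraw the protocol's adjusted analysis, so it cannot be read as abandoning it.

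All four points stand as limits on the concern. They do not remove the gap: the only SAP supplied has no adjusted analysis for any variable, and neither document says which estimate leads at the end.

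**Conclusion.** The concern holds in a modest form. The SAP leaves out the protocol's baseline-adjusted analysis, and the final analysis has no stated lead estimate. At 64 completers, adjusting the slope comparison is worth a net variance ratio of about 0.985 at the protocol's figures, about 0.94 if the SD of the change is 0.73, and about nil if all participants were selected on a slope above 3.0. The larger benefit may lie in secondary variables, at 14 to 24% lower variance, but that rests on an assumed r of 0.5 to 0.7. At the interim, adjustment brings no gain in precision unless the enrolled baseline SD is below about 0.8 with the SD of the change still 0.46.

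These figures assume equal variances at the two visits, a 7/8 interim split, and that the preliminary SDs of 1.3 and 0.46 apply to Aim 3 participants.

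**What to change.** - **Final analysis (protocol Section 6, Aim 3, and a final SAP).** Pre-specify as primary an ordinary least-squares model of change in slope on treatment arm and baseline slope. Report the adjusted difference with its 95% confidence interval. Modelling the 3-month slope instead gives the same treatment estimate. Keep the unadjusted t-test as a sensitivity analysis.
- **Secondary variables.** Use the same model, each with its own baseline value.
- **Interim (n = 15).** Keep the t-test as the lead analysis and report the baseline-adjusted estimate beside it.
- **Model form.** Do not copy the protocol's model as written, because it enters treatment group as both a fixed and a random effect. How the stratification factor enters is a separate question to settle in the same edit.

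The cost is a few sentences, one model statement, one degree of freedom, and the variance charge for estimating the baseline coefficient: about 1.7% at 64 completers and 9% at 15. No new data are needed. The change should be made before the final unblinding.

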# Plan for treatment assignment and randomization

Aims 1 and 2 of the study do not involve allocation to treatment groups.

Aim 3 is a randomized placebo-controlled double-blinded intervention study to examine the effect of metformin versus matching placebo on pulmonary vascular function. We anticipate enrolling 75 participants studied in Aims 1 and 2 who display abnormal pulmonary vascular hemodynamics into Aim 3. Participants with contraindications to metformin will be excluded as outlined in Table 1.

In order to allocate evenly, without bias, and in a manner blinded to both participants and investigators, we will randomize participants to treatment group (metformin versus placebo) with the assistance of the investigational drug pharmacy. Randomization will be performed in a 1:1 fashion in groups of 4 to assure balanced study groups, and will be stratified by type of pulmonary vascular dysfunction (resting or exercise-induced).

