Metformin or placebo administration: The participant will then receive, at random, either metformin or placebo in a 1:1 blinded fashion. Randomization will be stratified by type of PH (resting vs exercise-induced) and will be performed in blocks of 4 to assure balanced group sizes. Because we wish to ensure equal gender representation into the treatment and placebo groups, randomization will be done separately for men and women. Participants will be given 500mg capsules of metformin or matching placebo and instructed to take 500mg twice daily for 1 week, followed by 1g twice daily for a total of 3 months. Participants may receive study medication by mail or at study visits. We will exclude individuals with contraindications to metformin use as outlined in the exclusion criteria, and participants will be monitored for clinical symptoms of lactic acidosis and hypoglycemia. Medication compliance will be assessed with pill counts. The proposed use of metformin is IND-exempt.

Visit 3 (Interim): The third study visit will take place at MGH or remotely, approximately 2-4 weeks after initiation of metformin or placebo. An interim medical history will be taken by study staff in person or by telephone to assure that no contraindications to study participation or potential side effects have developed. Seated blood pressure and pulse may be obtained, and weight may be measured. Fasting blood work will be obtained at MGH or a local lab. We may collect up to 100 ml of blood for these measurements and storage of samples for future use.

Visit 4 (Interim): The fourth study visit will take place approximately 7-12 weeks after initiation of metformin or placebo. An interim medical history will be taken to assure that no contraindications to study participation or potential side effects have developed. Seated blood pressure, pulse, and anthropometrics will be obtained. Fasting blood work will be obtained. We will collect up to 100 ml of blood for these measurements and storage of samples for future use. Participants will undergo venous endothelial cell collection as outlined previously, as well as an electrocardiogram (ECG).

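### The SAP lets the observed variances choose between Welch's and the pooled t-test without a stated rule; naming Welch's test alone would prevent a possible drift from 5% when arms are small and unequal and the variances differ (minor)

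*SAP*

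**What the plan says.** The SAP, which is headed as the plan for an interim analysis, compares the change in PAP/CO slope between groups by intention to treat. The test is to be Welch's "t-test or Two independent samples t-test depending on the variances in both groups". Other hemodynamic and gas exchange variables follow the same procedure. The SAP adds that "P values are two-sided with a significance level of 0.05". It mentions 15 subjects but no arm sizes, and it does not say how the variances will be judged.

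The protocol (section 6, Statistical analyses for Aim 3) names one test: "We will apply a two-sample t-test to compare the delta in the two groups in an unadjusted intention-to-treat analysis". It does not say whether this is pooled or Welch. Its power paragraph uses one SD for both arms, "a standard deviation (SD) of the delta (12-week minus baseline) of 0.46".

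On allocation, section 4 of the protocol states "Randomization will be performed in a 1:1 fashion in groups of 4", stratified by type of pulmonary vascular dysfunction. Section 5 adds that "randomization will be done separately for men and women".

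**The concern.** The true variances are unknown, so the choice can rest only on the sample variances of the outcome. That raises two issues.

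- **Prespecification.** Two analysts could both follow the SAP, one with a formal variance test and one by eye, and report different primary p-values and intervals from the same data.
- **Level.** A variance test has little power in small samples, so the pooled test is often kept when the variances differ. If the arms are also unequal, the pooled test is too liberal when the smaller arm is the more variable one, and too conservative in the reverse case. The two-stage procedure inherits part of that error.

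At stake are the nominal 5% level and the coverage of the 95% interval for the primary comparison, and likewise for each secondary variable.

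**Working it through.** **1. The plan's own figure.** The protocol gives SD 0.46, a difference of 0.35, 75 enrolled and 15% loss.

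- Completers: 75 × 0.85 = 63.75, or 64, which is 32 per arm if even.
- Standardised difference: 0.35/0.46 = 0.761.
- Noncentrality: 0.761 × √(32/2) = 3.04.
- Power: Φ(3.04 − 1.96) ≈ 86% by the normal formula, 85.0% by the noncentral t.

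The stated power above 80% is reproduced. It assumes one SD and does not depend on which t-test is used.

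**2. Likely arm sizes at n = 15.** Blocks of 4 were simulated in four strata (dysfunction type by sex). With equal strata shares, the split is 8/7 in 75.1%, 9/6 in 23.1% and 10/5 in 1.8% of allocations. With shares of 50/25/15/10% it is 74.1%, 23.8% and 2.0%. With only two equal strata, 8/7 rises to 91.8% and 9/6 falls to 8.2%. The shares are assumptions, because the documents give none.

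**3. Level of the rule.** The simulation used normal data under the null and 400,000 trials per cell. The Monte Carlo standard error is √(0.05 × 0.95/400,000), about 0.035 percentage points. The assumed switch is an F-test at 5%: use Welch if it rejects, otherwise pooled. The SD ratios are also assumed. Entries are two-sided type I error in %; paired values are for SD ratios 1.5 and 2.

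| Arms | Test | Equal SDs | Larger SD in smaller arm | Larger SD in larger arm |
|---|---|---|---|---|
| 7/8 | two-stage | 4.9 | 5.6, 5.9 | 4.7, 4.7 |
| 7/8 | Welch | 4.7 | 4.9, 5.1 | 4.8, 4.9 |
| 6/9 | two-stage | 5.0 | 6.6, 7.3 | 4.0, 3.8 |
| 6/9 | Welch | 4.9 | 5.1, 5.2 | 4.8, 4.8 |
| 5/10 | two-stage | 5.1 | 7.9, 9.2 | 3.4, 3.0 |
| 5/10 | Welch | 5.1 | 5.4, 5.6 | 4.8, 4.8 |
| 26/38 | two-stage | 5.1 | 5.5, 5.1 | 4.7, 4.9 |
| 26/38 | Welch | 5.0 | 5.0, 5.0 | 5.1, 5.0 |

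At 32/32 both procedures give 5.0% throughout. A separate run gave 3.7% for the reverse case at 6/9.

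**4. Mechanism.** At 7/8 with the smaller arm having twice the SD, the F-test rejects in about 37% of trials, so the pooled test is kept in the other 63%.

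**5. Other switching rules.** Peak level over the SD ratios examined:

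| Switch | 7/8 | 6/9 | 5/10 | 26/38 |
|---|---|---|---|---|
| Variance ratio above 4 | 5.7 | 6.9 | 8.7 | 6.7 |
| Variance ratio above 2 | 5.3 | 5.6 | 6.5 | 5.4 |

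**6. How often the choice matters.** In null trials at 6/9 with twice the SD in the smaller arm, pooled and Welch disagree at the 5% level in 3.9% of trials.

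**The case against.** A reader might infer that the rule fails to hold 5% whenever arms are small or unequal. The results do not support that.

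- With equal true variances the F-test rule gives 4.9–5.1% at every split in the table.
- Small equal arms peak at about 5.5% (7/7).
- Unequal arms near the planned 64 completers reach at most about 5.5% under the F-test rule.

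A material excess needs three things together: small arms, unequal arms and the larger SD in the smaller arm. Nothing in the documents says that the variances will differ. The protocol assumes a single SD.

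The largest figures also belong to unlikely splits, and the more variable arm may equally be the larger one. Averaging both directions over the splits at SD ratio 2 gives 0.75 × (5.9 + 4.7)/2 + 0.23 × (7.3 + 3.8)/2 + 0.02 × (9.2 + 3.0)/2 ≈ 5.4%. That is under half a point above nominal. This stands as a statement about the design. It does not fully answer the point, because once the arms are known the level for that split is the relevant one.

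It is also fair to say that the SAP already provides for unequal variances by including Welch's test, and that it does not contradict the protocol, whose two-sample t-test could be either form. If the protocol meant the pooled test, the SAP's rule is an improvement on it. What remains is that the rule is undefined and that a simpler choice performs at least as well.

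**Conclusion.** The point holds as a minor one. The choice of primary test is data-driven and not fully specified; that follows from the SAP's text and needs no assumption. The effect on the level is conditional:

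- about 5% with equal true variances;
- 5.6–5.9% at the likeliest split of 15 (7/8);
- 6.6–7.3% at 6/9 and 7.9–9.2% at 5/10, when the smaller arm has 1.5 to 2 times the SD;
- about 3.7–4.0% at 6/9 in the reverse case.

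These figures rest on an assumed 5% F-test, assumed SD ratios, normal data and, for the split frequencies, assumed strata shares. The exact size of the SAP's procedure cannot be derived, because its rule is not stated; under a looser switch the excess is smaller. Welch's test alone stays at about 4.7–5.6% in the same settings.

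No consequence follows for a final analysis with 32 per arm. At 26/38 the excess is at most about half a point under the F-test rule, though a variance-ratio threshold of 4 would give 6.7%.

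**What to change.** Replace the clause in the SAP with: Welch's t-test, whatever the observed variances, for the primary and all secondary between-group comparisons. No preliminary variance test is then needed, and the analysis remains a two-sample t-test as the protocol describes.

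The cost is one clause and a slightly conservative level of 4.7% at 7/8 when variances are equal. For the protocol's difference of 0.35 and SD of 0.46, simulated power moves from 27.5% (pooled) to 26.6% (Welch) at 7/8, and is unchanged at 84.8% at 32/32.
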